6.2.1 Dosage

The dose selection (device frequency of 0.5 Hz and 100 μ A) is based on previous positive studies of the device for anxiety, depression, and insomnia. The dose selected is not detectable by the subject, so that adequate blinding can occur.

6.3 Assessment of Subject Compliance with Study Device Usage

Subjects will be provided with a tracking diary to record the start and stop time of daily usage, duration of usage, and any side effects if applicable. The research assistant will call every day during the first week of device treatment to ensure subjects are using the device, following instructions, and recording device usage times. Any reported side effects, additions or changes to medications or health care regime (i.e. non-pharmacological treatment), and adverse events will be noted. Subjects who note worsening of their anxiety or depression will be called by the study PI and if needed, they will be referred to their primary care or mental health provider for evaluation as appropriate, or if necessary for emergency treatment. During weeks 2-8 of device treatment, the research assistant will call once a week instead of daily.

6.4 Concomitant Medications/Treatments

Subjects who are treated for anxiety, depression, psychiatric or mental health must be on a stable regimen for the past 3 months. A concomitant medication report will be collected during each visit at OCNS.

Patients who add or change their medications or health therapy will be identified via weekly telephone check-up. We will allow necessary additions or changes in medications, specifically psychiatric medications, from the subject's personal provider except for the use of narcotics/opiates. Subjects who use narcotics/opiates after study enrollment will be withdrawn by PI upon PI notification.

Any subjects who express suicidal ideation will be referred to and followed up with their own primary care provider or psychiatric MD if they are able to contract for safety or to a psychiatric emergency department if they indicate a great risk of harm to themselves. In the absence of these, they will be referred to and followed up at a clinic/country medical system, which can provide proper care. All subjects sign a HIPAA or Release of Medical records if we feel this is a concern, enabling us to request past medical/psychiatric records if necessary.

No prohibitions will be made for changing health therapy but we will record and account for any changes in our analysis. We assume such changes in therapy will be uncommon but if they occur they will be equally balanced between the randomized groups.

While participating in this research study, subjects are not allowed to take part in any other research project. Simultaneous medications or treatments may invalidate the results of this research, as well as that of the other studies.

Changes in concomitant medication and any adverse events (see 9.1.1) are assessed at each visit, documented in subject's file, and reported to the PI for assessment.

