5.1 Subject Inclusion Criteria

In order to be eligible to participate in this study, an individual must meet all of the following criteria:

1. Male, Veteran or non-Veteran
2. Within the age range of 18-40 years old
3. On a stable regimen for anxiety, depression, psychiatric or mental health treatment (pharmacological or non-pharmacological) for the past 3 months
4. No active suicidal ideation or psychosis (including schizophrenia and bipolar disorder)
5. No uncontrolled or progressive severe medical illness (e.g., cancer, uncontrolled diabetes mellitus, active cardiac disease)
6. No use of a pacemaker or any other implanted electrical device
7. No alcohol consumption greater than 2 units daily
8. No daily use of illicit drugs or marijuana
9. Ability to independently complete the in-person study questionnaires and sign ICF without assistance
10. Willing to comply with all study procedures and be available for the duration of the study
11. No participation in another clinical trial study

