5.2 Subject Exclusion Criteria

An individual who meets any of the following criteria will be excluded from participation in this study:

1. Not male
2. Younger than 18 years old or older than 40 years old
3. Not on a stable regimen for anxiety, depression, psychiatric or mental health treatment (pharmacological or non-pharmacological) for the past 3 months

-
4. Active suicidal ideation or psychosis (including schizophrenia and bipolar disorder)
 5. History of inpatient treatment or suicidal ideation within the last year
 6. Use of a pacemaker or any other implanted electrical device
 7. Current alcohol and/or substance abuse of illicit drugs or marijuana
 8. Unable to independently complete the in-person study questionnaires and sign ICF due to impaired cognitive function
 9. Unwilling to comply with all study procedures
 10. Unavailable for the duration of the study
 11. Current participation in another clinical trial study
 12. Any other condition that the investigator believes would jeopardize the safety or rights of the subject or would render the subject unable to comply with the study protocol or make use of acquired data non-analyzable

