5.3 Strategies for Recruitment and Retention

Study participants will be recruited with flyers on UCLA and VA campuses, Internet web advertisements posted on non-interactive Facebook pages and Craigs List, and through direct contact from GLA VA physicians. Most subjects are expected to be recruited from the VA Physical Medicine and Rehabilitation clinic and from other primary providers in ancillary clinics at the VA. Physicians in these clinics are aware of this research study and will give information about who to contact if a Veteran is interested. Physicians will refer the potential study participants to the study team.

Subjects will be compensated for study participation as follows:

\$50.00 for completing screening visit 1, \$50.00 for completing the mid-study visit 2 and questionnaire completion, and \$100.00 for the final visit and completing the final set of questionnaires.

Only subjects who complete a minimum of 5 of 7 days per week compliance will be eligible to complete the final visit and thus be eligible for that payment. Subjects enrolled in study will be contacted weekly to assure subject compliance.

Parking will be provided at all visits.

The stipend payment subjects will receive will be up to \$200.00. If the subject withdraws from the study before finishing, that person will be paid for the study visits completed according to the schedule above.

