7 STUDY SCHEDULE

7.1 Prescreening

Potential subjects who respond to the study advertisement will undergo a brief (5 to 10 minute) phone screening by research assistant to assess potential eligibility prior to Visit 1. The prescreening will require potential subjects to respond verbally to approximately 10 yes/no medical history questions in order to determine whether a screening visit should be scheduled.

Subjects who seem eligible and available for the duration of the study will be scheduled for a screening visit at OCNS.

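### Section 6.4 mandates withdrawal for opiate use after enrolment without saying whether continuing use counts, no entry criterion names prescribed opiates, and no HADS follow-up is planned for those withdrawn

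*Combined protocol and SAP*

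**What the plan says.** Section 6.4 handles treatment changes during the study. It first permits most of them: "We will allow necessary additions or changes in medications, specifically psychiatric medications, from the subject's personal provider except for the use of narcotics/opiates". The next sentence sets the consequence for the exception: "Subjects who use narcotics/opiates after study enrollment will be withdrawn by PI upon PI notification". The same section has concomitant medication recorded at every visit, but attaches no eligibility decision to that record.

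None of the 11 inclusion items in 5.1 or the 12 exclusion items in 5.2 names opiates, narcotics or pain medication. The nearest are:

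- 5.1, item 3: "On a stable regimen for anxiety, depression, psychiatric or mental health treatment (pharmacological or non-pharmacological) for the past 3 months"
- 5.1, item 8: "No daily use of illicit drugs or marijuana"
- 5.2, item 7: "Current alcohol and/or substance abuse of illicit drugs or marijuana"
- 5.2, item 12: a catch-all that includes any condition the investigator believes "would render the subject unable to comply with the study protocol"

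After withdrawal, 5.6.2 provides for an adverse event report, return of the device and follow-up of adverse events. It mentions no HADS assessment. Section 5.3 opens the final visit only to subjects who used the device on at least 5 of 7 days per week. Section 10.2 nevertheless promises both intention-to-treat and completer analyses of the behavioural measures, and limits the biological measures to subjects with pre and post values.

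**The concern.** A mandatory withdrawal rule should match the entry criteria, so that nobody enters who already meets it. Here the rule turns on *use* after enrolment, while entry is silent on prescribed opiates. Two investigators could read 6.4 differently and treat the same continuing user differently.

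The situation is plausible in this population. Section 2.2 describes pain as a significant problem in Veterans, and 5.3 says "Most subjects are expected to be recruited from the VA Physical Medicine and Rehabilitation clinic", along with other VA providers.

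At stake are avoidable losses after randomisation in a small trial and, for opiates started on study, losses that may not be random. Section 2.2 links the intervention to reduced pain. If that link is real, the need for opiates could differ by arm. Section 6.4 expects therapy changes to be rare and balanced between groups, but that is an assumption.

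**Working it through.** **Step 1. Do the entry criteria screen for prescribed opiates?**

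| Item | What it covers | Does it stop a stable prescribed-opiate user? |
|---|---|---|
| 5.1 item 3 | Psychiatric or mental health regimen | No; analgesics are outside it |
| 5.1 item 8 | Daily illicit drugs or marijuana | No; illicit use only |
| 5.2 item 7 | Alcohol abuse; abuse of illicit drugs or marijuana | No; prescribed use is not named |
| 5.2 item 12 | Investigator's judgement | It can, but need not |
| 7.1 phone screen | Yes/no questions, content not in the documents | Unknown |
| 7.2 Visit 1 | Medical history reviewed | No opiate rule stated |

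**Step 2. What follows under each reading of 6.4?**

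- *Any use, including continuing use.* A stable user can pass 5.1 and 5.2, be randomised and meet the withdrawal rule at once. Opiate status at entry precedes randomisation, so it is balanced between arms in expectation. The cost is mainly sample size.
- *Only opiates started on study.* A stable user is unaffected. Someone who starts an opiate is removed after randomisation, for a reason that may relate to how they are doing or to their arm. An entry criterion would not prevent this.

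Under both readings the Week 8 HADS is lost, because 5.6.2 plans no outcome assessment and 5.3 closes the final visit to someone no longer using the device.

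**Step 3. Reproduce the plan's sample size (10.1).** Inputs: d = 0.80, one-sided alpha 0.05, equal groups (5.5). For n per group, the noncentrality is d × √(n/2), the degrees of freedom are 2n − 2, and power is the upper tail of the noncentral t beyond the critical value.

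- n = 21: noncentrality 2.592, df 40, critical t 1.684, power 0.817. This matches the printed 2.59 and t(40) = 1.68.
- n = 22: noncentrality 2.653, df 42, power 0.833.

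The stated 22 per group for 80% power is therefore reproduced to within one subject per group.

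**Step 4. Completers at the planned attrition (section 5).** 55 × 0.75 = 41.25, or about 20.6 per group, with power 0.810. The shortfall from 44 comes from the attrition arithmetic (44 × 1.25 = 55) and has nothing to do with opiates.

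**Step 5. Illustrate the extra loss.** The share affected is an assumption, and the calculation supposes that screening catches none of them.

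| Assumed share | Completers left | Power |
|---|---|---|
| 0% | 41.25 | 0.810 |
| 5% | 41.25 × 0.95 = 39.2 | 0.792 |
| 10% | 41.25 × 0.90 = 37.1 | 0.772 |
| 15% | 41.25 × 0.85 = 35.1 | 0.750 |

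Of 55 recruited, 5% to 15% is about 3 to 8 people. Some of them would have dropped out anyway, so the net loss is about 2 to 6 completers (41.25 × 0.05 = 2.1; 41.25 × 0.15 = 6.2).

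**The case against.** The strongest reply is context. The paragraph in 6.4 concerns patients who add or change medication, and the sentence before the rule carves opiates out of the permitted changes. The natural reading may well be that only opiates started on study trigger withdrawal. A stable user would then meet no rule and nothing would clash. This stands as a plausible intent, but the operative sentence speaks of use and does not limit itself to new use.

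A reader might infer that 5.1 and 5.2 contradict 6.4, or that opiate users are admitted and must then be removed. The documents do not support either. The entry lists are silent, which is a gap rather than a conflicting statement, and compulsory removal of continuing users is only one of two readings.

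Existing controls also count. Exclusion 12 lets the investigator turn away someone who could not comply. Medical history is reviewed at Visit 1, and the phone screen has "approximately 10 yes/no medical history questions", which may already ask about opiates. None of these is a stated criterion, so they weaken the point without removing it.

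It would also be wrong to treat the rehabilitation clinic as the sole main source. The sentence in 5.3 goes on to name other providers in VA ancillary clinics, and recruitment was later opened to non-Veterans. Section 13.2 reports 5 Veterans per group, so 14 of the 24 completers were non-Veterans.

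Finally, the mixed model in 10.2.1 can use a Week 4 score from someone withdrawn later. That helps only if such a score exists, and it relies on the missing Week 8 value being predictable from what was observed.

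**Conclusion.** The point holds as an ambiguity in 6.4, a missing matching entry criterion, and a lack of outcome follow-up for those withdrawn. It is a modest defect that is cheap to repair.

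The readable text gives neither opiate use at entry nor the number withdrawn under 6.4; the flow figure is not available. On the assumed 5% to 15%, power goes from about 81% to between 79% and 75%. The low end is negligible against the stated 80%. These figures describe the planned trial. The actual sample of 24 completers was set by recruitment.

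A reader might infer that removing people already on opiates at entry biases the comparison between arms. That does not follow, since their status is fixed before randomisation. The risk of informative loss attaches to opiates started on study. Missing Week 8 HADS data for the intention-to-treat analysis arises under either reading, and is the more important consequence.

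**What to change.** 1. Reconcile 6.4 with 5.1 and 5.2: state whether the rule covers continuing use or only opiates started on study, and align the entry lists so that no one is randomised who already meets a withdrawal rule. Which rule stands is for the sponsor's clinicians.
2. State in 5.6.2 that subjects taken off the device under 6.4 are still asked to complete the Week 4 and Week 8 HADS, and that they remain in the intention-to-treat analysis. Adjust 5.3 so that its compliance condition does not block that Week 8 assessment.
3. Since data collection is over, lost scores cannot be recovered. Report how many subjects were withdrawn under 6.4, by arm and time, and carry items 1 and 2 into any larger follow-on study.

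The cost is a short amendment, possibly one screening question, and a few extra questionnaires. Because 5.3 ties the final payment to the same compliance condition, that payment rule would need a line as well.

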7 STUDY SCHEDULE

7.1 Prescreening

Potential subjects who respond to the study advertisement will undergo a brief (5 to 10 minute) phone screening by research assistant to assess potential eligibility prior to Visit 1. The prescreening will require potential subjects to respond verbally to approximately 10 yes/no medical history questions in order to determine whether a screening visit should be scheduled.

Subjects who seem eligible and available for the duration of the study will be scheduled for a screening visit at OCNS.

7.2 Enrollment/Baseline Screening (Visit 1)

This visit will occur at the Oppenheimer Family Center for Neurobiology of Stress. It will take about 3 hours to complete the screening and device training process. The research team will verify OEF/OIF Veteran status (i.e. DD 214) before study enrollment if the subject identifies as a Veteran. The potential subjects will first review and sign ICF and HIPAA Authorization with either the RN, FNP, or MD. All are certified to obtain informed consent (nursing or physician license). Subjects will be identified by the PI, [name], as possibly eligible after the clinic visit and the study questionnaires have been completed and scored. Medical history will be reviewed and a physical will be performed as well. The assessment questionnaires include:

- A standardized psychiatric evaluation (MINI)
- Hospital Anxiety and Depression Scale (HADS)
- Mental Health Continuum Short Form (MHC-SF)
- Patient Reported Outcomes Measurement Information System (PROMIS-29)
- Positive and Negative Affect Schedule Short Form (PANAS-SF)
- Connor-Davidson Resilience Scale (CD-RISC)
- Perceived Stress Scale (PSS)
- Patient Health Questionnaire (PHQ)

-
- Columbia-Suicide Severity Rating Scale (C-SSRS) Self Report Screener - Recent

We will use the HADS to assess symptom severity defined as normal range (0-7), mild (8-10), moderate (11-14) or severe (15-20). Subjects with impaired emotional wellbeing as defined as a minimum combined HADS score of 14 will be included. Subjects who score >15 will be excluded in the study and will be given referrals to their personal provider or community mental health resources. (See “Reporting Suicidal Ideation” Section 5.4)

Subjects who express interest in participating and meet the inclusion criteria will be trained to use the CES device. They will be instructed that the device is set to a low level that should not be detectable. Subjects will have their first 1 hour treatment at OCNS (commencing Week 1 of the study). Subjects who tolerate the device treatment will then have blood drawn for baseline biological measures. They will be informed that this is a randomized controlled trial and they may or may not have an active device kit. Subjects will be sent home with a device, instructions for daily treatment, and a patient diary to track usage and side effects if applicable.

7.3 Intermediate Study Visit (Visit 2)

This visit will occur at the Oppenheimer Family Center for Neurobiology of Stress. This visit will take approximately 1 hour and will occur Week 4 ± 1 week. Subjects must complete this set of study questionnaires:

- Hospital Anxiety and Depression Scale (HADS)
- Positive and Negative Affect Schedule Short Form (PANAS-SF)
- Perceived Stress Scale (PSS)
- Columbia-Suicide Severity Rating Scale (C-SSRS) Self Report Screener - Since Last Contact
- Patient Reported Outcomes Measurement Information System (PROMIS-29)

Subjects will have vital signs and weight measured by a nurse. Adverse events and concomitant medication report will be collected as well. The study coordinator will collect the tracking diary for weeks 1-4 and provide another tracking diary to complete for weeks 5-8.

7.4 Final Study Visit (Visit 3)

This visit will occur at the Oppenheimer Family Center for Neurobiology of Stress. This visit will take approximately 2 hours and will occur after 8 weeks of

treatment, Week 8 + 1 week. Subjects will be asked to bring the CES device to return. The study coordinator will collect the tracking diary for weeks 5-8. The subjects must complete the final set of questionnaires:

- Mini International Neuropsychiatric Interview (MINI)
- Hospital Anxiety and Depression Scale (HADS)
- Mental Health Continuum Short Form (MHC-SF)
- Patient Reported Outcomes Measurement Information System (PROMIS-29)
- Positive and Negative Affect Schedule Short Form (PANAS-SF)
- Connor-Davidson Resilience Scale (CD-RISC)
- Perceived Stress Scale (PSS)
- Patient Health Questionnaire (PHQ)
- Columbia-Suicide Severity Rating Scale (C-SSRS) Self Report Screener - Since Last Contact
- Impression of Global Improvement Scale

The subjects will have vital signs and weight measured and have the final blood draw performed by a nurse. Adverse events and concomitant medication report will be collected as well.

8 STUDY PROCEDURES/EVALUATIONS

8.1 Study Procedures/Evaluations

Electronic assessment questionnaire data will be collected from subjects during the visits at UCLA OCNS using SurveyMonkey (www.surveymonkey.com) and unique subject identifiers. Survey Monkey states they utilize some of the most advanced technology for Internet security commercially available today. Unique usernames and passwords are required and must be entered each time a user logs on. When a user accesses secured areas of our site, Secure Sockets Layer (SSL) technology protects user information using both server authentication and data encryption, ensuring that user data is safe, secure, and available only to authorized persons. Servers are kept in a locked cage. Digital surveillance equipment monitors the data center. A firewall restricts access to all ports except 80 (http) and 443 (https). Intrusion detection systems and other systems detect and prevent interference or access from outside intruders. QualysGuard network security audits are performed weekly. McAfee SECURE scans performed daily.

The subjects will complete the aforementioned study questionnaires above (see “Study Schedule” Section 7) and the assessments will be scored per published guidelines.

All paper source data collected at UCLA will only contain unique subject ID numbers. Research staff will know matching of ID with subject for data collection purposes but this will not be written on documents in the field. The documents will be coded before being stored in subject’s file. Files will be secured in a locked cabinet in a locked room.

8.2 Laboratory Procedures/Evaluations

8.2.1 *Sample Draws*

Sample blood draws will be done by either the nurse coordinator or nurse practitioner. 8 mL BD Vacutainer® CPT™ Cell Preparation Tubes with Sodium Citrate will be used to store the blood draws. 8 mL of blood will be drawn during visit 1 and visit 3, so 16 mL of blood total will be drawn from each subject.

The blood draws will be performed at the OCNS clinic, [name], [name] and transferred immediately to the Inflammatory Biology Core (IBC) Laboratory, [name], for processing and storage.

8.2.2 ***Pre-Visit Sample Processing***

- Patient must be scheduled at least one week in advance by notifying through e-mail [name], [name], [name] with the following: patient ID, date, time point of visit (pre- or post-op), and estimated time of delivery of blood samples.
- If the new or rescheduled visit is less than one week away, please call [name] first at the IBC Lab [contact] or [name]) to confirm the ability of the lab to handle the specimens. When confirmed, then please email [name], [name], [name]
- Prepare tubes, labels (CES ID#, time point, and date), transport containers in advance

8.2.3 ***Study Visit Sample Processing***

1. Have the following tubes ready to be drawn in the following order:
 - i. 1 CPT tube, 8 mL (pick up as needed from IBC Lab)
2. Complete top portion of “CES Requisition Form” for IBC Lab
3. Have labels with participant’s study ID # and date ready
 - i. 1 x 8 mL CPT tube handling

BE SURE TO FILL CPT TUBE COMPLETELY.

Once the CPT tube is filled, **remove from blood draw apparatus and immediately but gently invert tube 8 to 10 times** to mix anticoagulant additive with blood. **DO NOT SHAKE.** Vigorous mixing can cause hemolysis. Place mixed tube upright in rack at room temperature in transport container; insure that container is closed to shield tube from light.

NOTE: Since this BD Vacutainer® CPT™ Tube contains chemical additives, it is important to prevent possible backflow from the tube with its attendant possibility of adverse reactions to the patient. To guard against backflow, the following precautions should be taken when drawing blood into the tube:

- Keep patient’s arm in the downward position during the collection procedure
- Hold the tube with the stopper uppermost
- Make sure the tube contents do not touch the stopper or the end of the needle during collection procedure

-
4. **Deliver ASAP to IBC lab by 4 p.m. at the latest**, [name] (main Lab):

- **Room temperature transport container**

- Place transport container containing rack with CPT and requisition form on black crate just inside door

If no lab staff is present in room 3160 where samples are dropped off, please check in room 3152 (opposite [name]'s office) to let someone know samples have arrived.

(If delayed after 4 p.m. and IBC Lab is closed, lavender top tubes may be held in refrigerator overnight and delivered to IBC Lab the next day; CPTs should be discarded)

Blood delivered to IBC Lab will be processed and stored for CPTs = PBMC (pellets for future Telomere and Telomerase)

